# 8.3.6. Concomitant therapy

# **8.3.6.1. Drug therapy**

For all drugs used during the observation period, the following information should be recorded. If an adverse event is noted, the drugs used during the period from the start date of administration to the onset of the adverse event and medications used for treatment of the adverse event should also be recorded.

- 1. Drug name (product name)
- 2. Route of administration
- 3. Period of administration
- 4. Reasons for administration (infections caused by SARS-CoV-2, complications, adverse events, other)

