#### 8.3.10. Adverse events

Occurrence of adverse events from the start date of administration of this drug to the end date of the observation period should be confirmed and the following information should be recorded.

Also, further investigation should be separately conducted, if deemed necessary by Sponsor for patients who experienced a serious adverse reaction, an unexpected adverse reaction or other adverse reactions not listed in the package insert.

- Presence/absence of adverse event
- Name of adverse event
- Date of occurrence
- Intervention
- Seriousness
- Outcome
- Causal relationship to this drug

If the adverse event is associated with abnormal laboratory values, i.e., clinical laboratory tests, the following information should also be recorded.

- Date of tests
- Name of laboratory test
- Site reference value
- Site unit
- Test results

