5.4. Subgroups

Subgroup analyses of safety will be performed for the following patient characteristics. Descriptions in brackets indicate the levels of subgroups, and the underlined level indicates the standard level for calculation of risk ratio.

- Hepatic impairment [absent, present, unknown]
- Hepatic impairment [absent, mild, moderate, severe, unknown (presence unknown or severity unknown)]
- Renal impairment [absent, present, unknown]
- Renal impairment [absent, mild, moderate, severe, unknown (presence unknown or severity unknown)]
- Age [<15 years, ≥15 years]
- Age [\leq 65 years, \geq 65 years]
- Age [<18 years, ≥18 years]
- Age [\leq 65 years, \geq 65 to \leq 75 years, \geq 75 years]
- Pregnancy [absent, present] * Female only

Subgroup analyses of safety will be performed for the following other factors:

Contraindications for coadministration/precautions for coadministration [both absent, precautions for coadministration present, contraindications for coadministration present] Patients with precautions for coadministration and patients with contraindications for coadministration may overlap. For patients with precautions for coadministration and patients with contraindications for coadministration, events after the start of coadministration will be included.

• Complicated with HIV infection and concomitantly using anti-HIV therapy including ritonavir or cobicistat [absent, present] * Specifically, patients concomitantly using ritonavir or cobicistat will be classified as present and other patients as absent.

Patients possibly contraindicated in the package insert of this drug (hereinafter referred to as contraindicated patients) will be extracted based on separately specified criteria and subgroup analysis of safety will be performed.

Subgroup analyses of efficacy will be performed for the following patient characteristics. Unless otherwise specified, analysis will be performed for Efficacy Analysis Sets 1 and 3. Descriptions in brackets indicate the levels of subgroups, and the underlined level indicates the standard level for calculation of risk ratio and hazard ratio.

- Combination of admission status at the start of treatment with this drug [inpatient, outpatient] and risk factors for aggravation [risk factors present, risk factors absent, risk factors unknown]. To be performed in Efficacy Analysis Set 1.

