6. ENDPOINTS AND COVARIATES

6.1. Safety Endpoints

The safety evaluation period is defined as the observation period in Section 2.2. The number of days from the start date of treatment to the onset date of event will be calculated as [event onset date – start date of treatment with this drug + 1].

- Adverse reactions: Adverse events for which the causal relationship was considered as related by the treating physician
- Adverse events: All-causality adverse events
- Serious adverse events or serious adverse reactions: Adverse events or adverse reactions considered by the treating physician to be serious
- Events to be handled as safety specifications are specified separately.

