8.1.3. Binary variables

For binary variables, patients falling into each binary category will be summarized in terms of frequency and proportion. When a confidence interval is calculated for a proportion, the two-sided 95% confidence interval (exact method) will be calculated.

When a comparison for proportion is made between subgroups, the risk ratio and its 95% confidence interval will be calculated. In addition, the risk ratio and its 95% confidence interval will be graphically presented.

If a test is performed, Fisher's exact test will be used for the relationship with nominal scale data and Cochran-Armitage test (exact method) for the relationship with ordinal scale data. However, if it is difficult to perform the exact method, a chi-square test or Cochran-Armitage test with normal approximation will be used as an alternative to the exact method.

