8.2.3. Safety analysis

Refer to Section 6.1 for the evaluation period for adverse reactions and adverse events. The listing will include all events reported in this study.

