8.2.3.3. Subgroup analyses

The number and proportion of patients who experienced at least 1 adverse reaction will be tabulated by factor specified in Section 5.4. In addition, risk ratios of the incidence of adverse reactions between subgroups will be calculated as described in Section 8.1.3. However, if there is a category with less than 10 patients and it is determined difficult after reconsideration of the classification of categories, the risk ratio for the category will not be calculated. Similar analyses will be performed for adverse reactions with PTs of dysgeusia, taste disorder, diarrhoea, vomiting, nausea, decreased appetite, and rash by each of the following factors.

Descriptions in brackets indicate the levels of subgroups, and the underlined level indicates the standard level for calculation of risk ratio.

- Hepatic impairment [absent, present, unknown]
- Hepatic impairment [absent, mild, moderate, severe, unknown (presence unknown or severity unknown)]
- Renal impairment [absent, present, unknown]
- Renal impairment [absent, mild, moderate, severe, unknown (presence unknown or severity unknown)]
- Age [<15 years, \ge 15 to <65 years, \ge 65 years]
- Age [<18 years, ≥18 years]
- Age [\leq 65 years, \geq 65 to \leq 75 years, \geq 75 years]
- Pregnancy [absent, present] * Female only
- Contraindications for coadministration/precautions for coadministration [both absent, precautions for coadministration present, contraindications for coadministration present] Patients with precautions for coadministration and patients with contraindications for coadministration may overlap. For patients

with precautions for coadministration and patients with contraindications for coadministration, events after the start of coadministration will be included.

 Complicated with HIV infection and concomitantly using anti-HIV therapy including ritonavir or cobicistat [absent, present] * Specifically, patients concomitantly using ritonavir or cobicistat will be classified as present and other patients as absent.

Adverse reactions will be summarized in terms of number and proportion by each of the following factors among the factors specified in Section 5.4 for each SOC and PT.

- Hepatic impairment [absent, present]
- Hepatic impairment [absent, mild, moderate, severe]
- Renal impairment [absent, present]
- Renal impairment [absent, mild, moderate, severe]
- Age [<15 years, \ge 15 to <65 years, \ge 65 years]
- Age [<18 years, \ge 18 years]

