- Age [<65 years, ≥65 to <75 years, ≥75 years]
- Pregnancy [absent, present] * Female only
- Contraindications for coadministration/precautions for coadministration [both absent, precautions for coadministration present, contraindications for coadministration present] Patients with precautions for coadministration and patients with contraindications for coadministration may overlap. For patients with precautions for coadministration and patients with contraindications for coadministration, events after the start of coadministration will be included.
- Complicated with HIV infection and concomitantly using anti-HIV therapy including ritonavir or cobicistat [absent, present] * Specifically, patients concomitantly using ritonavir or cobicistat will be classified as present and other patients as absent.

A listing of adverse reactions will be prepared for contraindicated patients.

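### The co-medication risk ratio counts reactions over different windows in the levels it compares, so it is not like for like if a listed drug starts after the first dose

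*SAP*

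**What the plan says.** SAP 5.4 defines a safety factor with three levels: neither kind of listed co-drug, precautionary co-drug present, and contraindicated co-drug present. The last two may overlap. For those two only, the SAP adds: "For patients with precautions for coadministration and patients with contraindications for coadministration, events after the start of coadministration will be included". SAP 8.2.3.3 repeats the rule for the seven named PTs and for the SOC/PT tables.

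The level with neither co-drug has no rule of its own, so the general one in SAP 6.1 applies: "The safety evaluation period is defined as the observation period in Section 2.2". That period runs from the first dose to Day 28 after the end of treatment (SAP 2.2).

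On the comparison, SAP 8.2.3.3 says: "The number and proportion of patients who experienced at least 1 adverse reaction will be tabulated by factor specified in Section 5.4", with risk ratios calculated as in SAP 8.1.3: "When a comparison for proportion is made between subgroups, the risk ratio and its 95% confidence interval will be calculated". Neither section uses person-time or time-dependent exposure, and nothing limits the factor to drugs in use at the first dose.

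Protocol 8.3.6.1 collects every drug used in the observation period, with its period of administration and its reason: "Reasons for administration (infections caused by SARS-CoV-2, complications, adverse events, other". For each adverse event, Protocol 8.3.10 collects "Date of occurrence".

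**The concern.** The rule has a sound purpose: a reaction that came before a co-drug should not be attributed to it. It has an effect only when a listed drug starts after the first dose, and in that case it makes the event windows unequal.

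Two mechanisms act in different ways.

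- **Start unrelated to reactions.** Early reactions are dropped from the *present* numerator while the patient stays in its denominator. The ratio is biased downward.
- **Start triggered by a reaction.** The patient also leaves the level with neither co-drug and takes a case with them, so the reference risk falls. The net bias can go either way.

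The product contains a potent CYP3A4 inhibitor (Protocol 6), and this is the planned comparison of reaction risk by contraindicated or precautionary co-medication. A ratio near 1 could mean no effect, a masked effect or two biases that cancel, and the table alone would not show which.

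**Working it through.** The documents give no figure for this ratio, so there is none to reproduce.

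**Inputs from the documents:** 3000 patients and a 7.8% reaction incidence (Protocol 8.5); 5 dosing days plus 28 days, so 33 days.

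**Assumptions:** everything else. The level with neither co-drug is taken as the reference, because the underlining is not visible in the text supplied. The true ratio R is 1.00 unless stated.

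**1. Starts unrelated to reactions.** Let *f* be the late-start share of the *present* level and *m* the mean probability that onset falls on or after the co-drug start day. The planned ratio is R × [(1 − f) + f·m]. Onset is either uniform over 33 days, or 80/20 (0.16 per day on Days 1–5, 0.2/28 per day on Days 6–33). With f = 0.25:

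| Onset | Co-drug starts | m | Planned ratio | If 30% of reactors have a second reaction |
|---|---|---|---|---|
| uniform | Days 2–5 | 0.924 | 0.98 | 0.99 |
| 80/20 | Days 2–5 | 0.600 | 0.90 | 0.92 |
| uniform | Days 1–33 | 0.515 | 0.88 | 0.90 |
| 80/20 | Days 1–33 | 0.191 | 0.80 | 0.81 |

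The last column replaces m by m + 0.3(1 − m)m. The Days 1–33 rows apply only if a drug started after the last dose counts as coadministration. With f = 0 the ratio is 1.00. If *after* excludes a reaction on the co-drug start date, the second row has m = 0.44 and the ratio falls from 0.90 to 0.86.

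**2. Starts triggered by a reaction.** Let k = 20 reactors start a listed drug after their reaction date, with no second reaction. P patients are otherwise *present*, and A = 3000 − P. The planned ratio is [0.078P/(P + k)] / [(0.078A − k)/(A − k)].

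- P = 100: (7.8/120)/(206.2/2880) = 0.91
- P = 300: (23.4/320)/(190.6/2680) = 1.03
- P = 1000: (78/1020)/(136/1980) = 1.11

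**3. Both together.** With 750 users at first dose, 250 unrelated late starters (m = 0.6) and 20 triggered starters: [(58.5 + 250 × 0.078 × 0.6)/1020]/(136/1980) = (70.2/1020)/(136/1980) = 1.00. The two biases cancel by chance.

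**4. Alternatives.**

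- *Levels fixed at first dose, full window:* 1.00 in all three cases; for example (78/1000)/(156/2000) in case 2 with P = 1000. The cost is dilution, R/[1 + g(R − 1)m]. With R = 1.5, g = 250/2250 and m = 0.6 this is 1.45. The planned rule gives 1.5 × 0.90 = 1.35.
- *Exclude late starters* (case 2): 0.078/(136/1980) = 1.14 with P = 1000, and 1.09 with P = 100.
- *Drop the limit but keep the levels* (case 2): (98/1020)/(136/1980) = 1.40 with P = 1000, and 3.24 with P = 100.
- *Crude person-day rate ratio* (80/20 onset, starts on Days 2–5, f = 0.5): [(0.5 + 0.5 × 0.6)/(0.5 × 33 + 0.5 × 30.5)]/(1/33) = 0.83, where the plan gives 0.80.

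**5. Simulation.** A day-level simulation with no true effect, about 53% of reactions by Day 5 and various mixes of late and triggered starts gave 0.67 to 1.26 under the SAP rule. Levels fixed at first dose gave 0.99 to 1.00, and a day-stratified time-dependent ratio gave 0.99 to 1.01.

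**The case against.** The strongest reply is about weight. The bias needs listed drugs started after the first dose and late starters kept in the denominator, and the documents state neither. The 0.80 and 0.88 figures need starts as late as Day 33 to count as coadministration with a 5-day course. With starts on Days 2–5 and 10% late starters, the ratio is only 0.96 to 0.99. The triggered case depends on a drug list that is not in the documents. With k = 5 instead of 20 the ratios are 0.97, 1.01 and 1.03. Sampling error is larger than most of this: with no effect, the approximate 95% interval is 0.77 to 1.30 with 1000 *present* patients and 0.50 to 1.98 with 100. The analysis is exploratory with no decision rule (SAP 4), and it is unadjusted in a one-arm study.

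There is also a fair point about the remedy. Fixing levels at first dose puts a patient who starts a listed drug on Day 2 in the reference level, whereas the current rule asks about reactions under actual co-exposure. The SAP history gives the study status at version 5 as completed, so a change now may be post hoc.

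All of this limits the size and priority of the point. It does not remove the unequal windows: wide intervals do not correct bias, and the separate analysis of contraindicated patients in SAP 5.4 does not correct this ratio. The co-exposure question can be kept as a separate table.

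**Conclusion.** The concern holds. As written, the risk ratio for this factor is not like for like whenever a listed drug starts after the first dose, which is the only situation in which the rule does anything. The bias can go either way: 0.80 to 1.11 in the worked null cases and 0.67 to 1.26 in the simulation. It is zero if every listed drug is already in use at the first dose. These figures rest on assumed late-start shares, onset patterns and numbers of triggered starts. The full window for the reference level is inferred from the general definition in SAP 6.1.

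This is an optional improvement, with medium confidence in its practical weight. The overall SOC/PT tables, the contraindicated-patient listing and the separate ritonavir/cobicistat factor are unaffected. So are the listings, for which SAP 8.2.3 says "The listing will include all events reported in this study".

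**What to change.** In SAP 5.4 and 8.2.3.3:

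- For the risk ratio, classify every patient by listed co-drug use at the first dose. Keep later starters in that level rather than excluding them, and count reactions over the full observation period in all levels.
- To keep the purpose of the current rule, tabulate late starters' reactions before and after the co-drug start separately. Alternatively, fit a time-dependent exposure model for time to first reaction, with day since first dose as the time scale.
- State the denominator, the exposure window (including whether a start after the last dose counts), the reference level, and how a reaction on the co-drug start date is counted.

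The cost is SAP wording and modest programming; the drug periods and event dates are already collected. The *present* levels become smaller, so intervals widen and the rule in SAP 8.2.3.3 for categories under 10 patients is met more often. Late starters slightly dilute the reference level. If the planned ratio has already been produced, report the first-dose version beside it and label it post hoc.

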6. ENDPOINTS AND COVARIATES

6.1. Safety Endpoints

The safety evaluation period is defined as the observation period in Section 2.2. The number of days from the start date of treatment to the onset date of event will be calculated as [event onset date – start date of treatment with this drug + 1].

- Adverse reactions: Adverse events for which the causal relationship was considered as related by the treating physician
- Adverse events: All-causality adverse events
- Serious adverse events or serious adverse reactions: Adverse events or adverse reactions considered by the treating physician to be serious
- Events to be handled as safety specifications are specified separately.

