#### 2. Method of analysis

• Analysis for safety evaluation

Events possibly related to this drug are considered as adverse reactions. The number of patients with adverse reactions and the proportion [(%): number of patients with adverse reactions / number of patients included in the safety analysis set] will be calculated.

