#### 10.3. Causality assessment

The investigator is required to assess and record the causal relationship. For all AEs, sufficient information should be obtained by the investigator to determine the causality of each AE. For AEs with a causal relationship to this drug, follow-up by the investigator is required until the event and/or its sequelae resolve or stabilize at a level acceptable to the investigator, and Pfizer concurs with that assessment.

An investigator's causality assessment is the determination of whether there exists a reasonable possibility that this drug caused or contributed to an AE. If the investigator's final determination of causality is "unknown" and s/he cannot determine whether this drug caused the event, the safety event must be reported within 24 hours.

If the investigator cannot determine the etiology of the event but s/he determines that this drug did not cause the event, this should be clearly documented on the CRF and the NIS AEM Report Form.

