7. HANDLING OF MISSING DATA

If the seriousness, causal relationship, treatment, and outcome of an adverse event are missing, the data will be handled as "unknown" for tabulation.

If there are no measured values within the acceptable window for each time point of evaluation of efficacy endpoints (Appendix 2), the values will be handled as missing and will not be imputed. Definitions of acceptable windows for other endpoints are provided in Appendix 2.

If the date of admission is missing or partial, the last complete date among the following will be used as the imputed date.

- Start date of this drug
- The first day of the month of the same month as the date of admission (if the day of admission is missing and the month and year are available)
- The first day of the year of the same year as the date of admission (if the month and day of admission are missing and the year is available)

If the date of death and the date of last observation are missing or partial, the latest complete date among the following will be used as the imputed date.

- Start date/end date of this drug
- Start date/end date of concomitant drug therapy
- Start date/end date of concomitant non-drug therapy
- Viral test
- Date of measurement of body temperature/SpO₂
- Date of admission/date of discharge
- Date of efficacy evaluation (date of the highest severity/date of evaluation at the end of the observation period)
- Date of onset of adverse event, resolution/recovery of adverse event, date of death
- The first day of the month of the same month as the date of last observation (if the day of last observation is missing and the month and year are available)
- The first day of the year of the same year as the date of last observation (if the month and day of last observation are missing and the year is available)

The policy for handling uncleaned data is described below.

- Items of missing data: Values will be handled as missing (category of categorical variables is "not recorded") in both tabulation and listing.
- Items of inconsistent data: Inconsistent data will be handled as missing in both tabulation and listing. However, a list of data handling will be prepared separately.
- No signature: The descriptions in the CRF without the signature of the contract physician (including the case of only the signature of a physician other than the contract physician) will be handled as missing in both tabulation and listing.

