8.2.3.1.3. Details of adverse reactions

Adverse reactions will be summarized by SOC and PT in terms of number and proportion by each of the following factors:

- Seriousness [serious, non-serious]
- Known/unknown [known, unknown]
- Action taken [permanent discontinuation, temporary discontinuation or dose reduction]
- Outcome [fatal, not recovered, recovered with sequelae, improved, resolved/recovered, unknown]
- Outcome [fatal]

Multiple adverse reactions of the same PT occurring in the same patient will be handled as follows:

• Seriousness: If both serious and non-serious reactions of the same PT occurred in the same patient, the patient will be counted as one with serious reaction.

- Known/unknown: If both known and unknown reactions of the same PT occurred in the same patient, the patient will be counted as one with unknown reaction.
- Action taken: If multiple actions were taken for adverse reactions of the same PT, only one category of action will be adopted with "permanent discontinuation," "temporary discontinuation or dose reduction," and "dose increase or no change" being given priority in this order.
- Outcome: The outcome for the last event will be adopted.

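### Read literally, the SAP leaves adverse events of unknown or missing causality out of the adverse reaction count, and no full-set incidence table by SOC and PT shows them

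*SAP*

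**What the plan says.** Four places bear on the numerator of the main safety result.

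- **Protocol 8.7** sets the rule "Events possibly related to this drug are considered as adverse reactions" and gives the incidence as "number of patients with adverse reactions / number of patients included in the safety analysis set".
- **SAP 6.1** defines adverse reactions as "Adverse events for which the causal relationship was considered as related by the treating physician".
- **SAP 7** covers gaps: "If the seriousness, causal relationship, treatment, and outcome of an adverse event are missing, the data will be handled as" unknown, for tabulation. It also treats inconsistent entries as missing.
- **Protocol 10.3** describes the causality assessment as the "determination of whether there exists a reasonable possibility that this drug caused or contributed to an AE". It allows 'unknown' as a final answer: where the investigator "cannot determine whether this drug caused the event, the safety event must be reported within 24 hours". A separate sentence covers the investigator who cannot name the cause but concludes that the drug was not responsible; that conclusion is to be documented as such.

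Neither document says whether an event with unknown or missing causality counts as an adverse reaction in the analysis.

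**The concern.** The SAP definition asks for a positive judgement. A physician who recorded 'unknown', or recorded nothing, has not considered the event related. A programmer following SAP 6.1 to the letter would therefore treat such an event exactly like one that the physician had attributed to another cause. Protocol 10.3 does not treat those two situations alike.

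The patient stays in the denominator. SAP 5.1 removes patients for whom no adverse event information was reported at all, not patients with a recorded event whose causality field is empty. Each such patient without another reaction therefore counts as reaction-free.

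Adverse reaction incidence is the basis of the sample size (protocol 8.5.2, SAP 2.2). Protocol 15 makes a suggested serious unknown reaction, or a marked rise in reaction frequency, a reason to consider revising the package insert or starting a new study. A numerator that can only err low is awkward for that purpose.

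**Working it through.** **Step 1. Where could such an event appear?**

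| SAP section | Content | Shows events of unknown or missing causality? |
|---|---|---|
| 8.2.3.1.1, 8.2.3.1.2 | All and serious adverse reactions by SOC and PT | No, on the 6.1 definition |
| 8.2.3.1.3 | "Adverse reactions will be summarized by SOC and PT in terms of number and proportion by each of the following factors": seriousness, known/unknown, action taken, outcome | No; causality is not a factor, and known/unknown is a separate factor from causality |
| 8.2.3.1.4, 8.2.3.3 | Timing and outcome; subgroups | No; adverse reactions only |
| 8.2.3.1.5 | Safety specifications | Placed under the adverse reactions heading; named risks only |
| 8.2.3.2.1 | All-causality events by SOC and PT | Yes, but in the consented set only, and non-serious events may be cut by an incidence threshold |
| 8.2.3, 9 | Listings | Yes, as individual cases without an incidence |

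**Step 2. Reproduce the plan's own figures.** Inputs from protocol 8.5.2: N = 3000, incidence 7.8%, at least 214 patients with probability 90%, and at least one case of a 0.1% reaction with probability 95%.

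- For X ~ Bin(3000, 0.078) the mean is 3000 × 0.078 = 234. The exact tail gives P(X ≥ 214) = 0.920, P(X ≥ 215) = 0.909 and P(X ≥ 216) = 0.897. The stated 214 is met.
- For one case at 0.1%, n = ln(0.05)/ln(0.999) = 2994.2, so 2995. At N = 3000 the probability is 1 − 0.999^3000 = 0.9503.

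Both figures stand.

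**Step 3. Sensitivity to the literal rule.** Let u be the share of patients with a true reaction who are lost because their causality is coded unknown or missing. The documents give no value for u, so the range below is an assumption. The observed incidence is 7.8% × (1 − u), and the rare reaction is taken to lose the same share: 0.1% × (1 − u).

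| u (assumed) | Observed incidence | Expected patients | P(X ≥ 214) | P(at least 1 case) | n for 95% |
|---|---|---|---|---|---|
| 0 | 7.80% | 234.0 | 0.920 | 0.950 | 2995 |
| 2% | 7.64% | 229.3 | 0.862 | 0.947 | 3056 |
| 5% | 7.41% | 222.3 | 0.728 | 0.942 | 3152 |
| 10% | 7.02% | 210.6 | 0.414 | 0.933 | 3328 |

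P(X ≥ 214) falls steeply because 214 lies close to the expected count, so the incidence column is the fairer measure of size. For scale, the 95% half-width at N = 3000 is 1.96 × √(0.078 × 0.922/3000) = 0.96 points, and the loss at u = 10% is 7.80 − 7.02 = 0.78 points. The bias would thus be smaller than the sampling error over this range, but it runs in one direction and more patients would not remove it.

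**The case against.** The strongest reply is that the two definitions do not conflict. Under the reasonable-possibility standard of protocol 10.3, an event judged related is already one that is possibly related. The CRF item in protocol 8.3.10 is simply the causal relationship to the drug, and neither document shows a graded scale with a separate 'possibly' level. This stands. A reader might infer from the two wordings that the SAP narrowed the protocol's definition for judged events; the documents do not support that.

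A reader might also take the 24-hour rule to mean that the protocol counts 'unknown' as a reaction. It does not say so. The rule governs reporting, and protocol 10.1 applies the same deadline to all serious adverse events whatever their cause.

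Third, the SAP nowhere states that these events are excluded; exclusion follows from reading 6.1 literally. That is correct. It leaves the headline numerator depending on how a programmer reads the definition.

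Fourth, the events are not hidden. They are in the listings, those with an undetermined cause go to the sponsor within 24 hours, and all-cause death is analysed in the efficacy sets (SAP 8.2.4.5). Investigators must also assess causality and answer queries, so the number may be small. All of this stands, and it rules out any claim that a signal would be lost. A listing still does not supply an incidence.

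Finally, counting every such event as a reaction can push the incidence up in a single-arm study where worsening of the disease is itself an adverse event (protocol 10.4). This is fair, and it is the reason to report both figures.

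**Conclusion.** The point holds for adverse events with unknown or missing causality, and only for those. Applied as written, SAP 6.1 and 7 keep them out of the adverse reaction numerator, and no SOC/PT incidence table in the full safety analysis set shows them. Any bias is downward.

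Its size cannot be determined from the documents. With an assumed 0 to 10% of true reactions coded unknown or missing, 7.8% becomes 7.8 to 7.0%. This assumes that those events are true reactions in patients with no other counted reaction. A reader might multiply an assumed 20% adverse event incidence by an assumed 5 to 10% unknown-only share and arrive at a loss of 1 to 2 points. Neither input is in the documents, so that figure should not be used.

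The sample size calculation itself is sound, and nothing here calls for more patients.

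**What to change.** 1. In SAP 6.1, align with protocol 8.7 by defining adverse reactions as adverse events whose relationship to this drug is not ruled out, including those with unknown or missing causality. Carry the definition through the adverse reaction and subgroup tables.
2. Report the related-only incidence beside it, as a second line or column.
3. Add a table of the number of events with unknown or missing causality by SOC and PT in the full safety analysis set, not only in consented patients.

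The cost is one definition, one extra column and one short table, all from causality data already collected under protocol 8.3.10. The downside is that the stated incidence may be slightly higher and may include some events of the disease itself. The related-only line makes that visible. Because the documents do not say how unknown causality was handled in the 7.8% benchmark, having both lines also helps any comparison with it.
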